8.3 ADVERSE EVENTS AND SERIOUS ADVERSE EVENTS

8.3.1 DEFINITION OF ADVERSE EVENTS

Adverse event means any untoward medical occurrence associated with the use of an intervention in humans, whether or not considered intervention-related (21 CFR 312.32 (a)).

8.3.2 DEFINITION OF SERIOUS ADVERSE EVENTS

An adverse event (AE) or suspected adverse reaction is considered "serious" if, in the view of the PI, it results in any of the following outcomes: death, a life-threatening adverse event, inpatient hospitalization or prolongation of existing hospitalization, a persistent or significant incapacity or substantial disruption of the ability to conduct normal life functions, or a congenital anomaly/birth defect. Important medical events that may not result in death, be life-threatening, or require hospitalization may be considered serious when, based upon appropriate medical judgment, they may jeopardize the participant and may require medical or surgical intervention to prevent one of the outcomes listed in this definition. Examples of such medical events include allergic bronchospasm requiring intensive treatment in an emergency room or at home, blood dyscrasias or convulsions that do not result in inpatient hospitalization, or the development of drug dependency or drug abuse.

8.3.3 CLASSIFICATION OF AN ADVERSE EVENT

8.3.3.1 SEVERITY OF EVENT

The following guidelines will be used to describe severity.

- **Mild** Events require minimal or no treatment and do not interfere with the participant's daily activities.
- **Moderate** Events result in a low level of inconvenience or concern with the therapeutic measures. Moderate events may cause some interference with functioning.
- Severe Events interrupt a participant's usual daily activity and may require systemic drug therapy or other treatment. Severe events are usually potentially life-threatening or incapacitating. Of note, the term "severe" does not necessarily equate to "serious".

8.3.3.2 RELATIONSHIP TO STUDY INTERVENTION/EXPERIMENTAL MANIPULATION

All AEs must have their relationship to study intervention assessed by the PI. She will evaluate the event based on temporal relationship of the event to the study intervention or research procedures, and her clinical judgment. The degree of certainty about causality will be graded using the categories below.

- **Definitely Related** There is clear evidence to suggest a causal relationship, and other possible contributing factors can be ruled out. The clinical event, including an abnormal laboratory test results, occurs in a plausible time relationship to participation in the study intervention and cannot be explained by other factors (e.g. concurrent disease, other treatments or activities or action).
- Probably Related There is evidence to suggest a causal relationship, and the influence of other factors is unlikely. The event occurs within a reasonable time relative to participation in the study intervention, is unlikely to be attributed to concurrent disease or other factors.
- **Potentially Related** There is some evidence to suggest a causal relationship (e.g., the event occurred within a reasonable time relative to participation in the study intervention). However, other factors may have contributed to the event (e.g., the participant's clinical condition, other concomitant events). Although an AE may rate only as "possibly related" soon after discovery, it can be flagged as requiring more information and later be upgraded to "probably related" or "definitely related", as appropriate.
- Unlikely to be related A clinical event whose temporal relationship to participation in the study intervention makes a causal relationship improbable (e.g., the event did not occur within a reasonable time after administration of the study intervention) and in which underlying disease or other factors provide a plausible explanation for the event occurrence.
- Not Related The event is completely independent of the study intervention, and/or evidence exists that the event is definitely related to another reason.

8.3.3.3 EXPECTEDNESS

The primary investigator will be responsible for determining whether an AE is expected or unexpected. An AE will be considered unexpected if the nature, severity, or frequency of the event is not consistent with the risk information previously described for the study intervention.

8.3.4 TIME PERIOD AND FREQUENCY FOR EVENT ASSESSMENT AND FOLLOW-UP

The occurrence of an AE or SAE may come to the attention of the study team during study visits and routine study participant contact throughout their participation in the study.

All AEs including (including SAEs) will be captured on the appropriate CRF. Information to be collected includes event description, date of onset, PI's assessment of severity, relationship to study intervention, and time of resolution/stabilization of the event. All AEs occurring while on study must be documented appropriately regardless of relationship. All AEs will be followed to adequate resolution.

Any medical condition that is present at the time that the participant is screened will be considered as baseline and not reported as an AE. However, if the study participant's condition related to their NAFLD/NASH deteriorates at any time during the study, it will be recorded as an AE. Changes in condition in unrelated medical issues with be documented but not reported.

each study visit, the investigator will inquire about the occurrence of AE/SAEs since the last visit. Events will be followed for outcome information until resolution or stabilization.

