2.3 RISK/BENEFIT ASSESSMENT

2.3.1 KNOWN POTENTIAL RISKS

The risks related to dietary changes and increase in physical activity are minimal, with overall systemic benefit improvements likely far outweighing any potential risks. So long as dietary restriction does not involve > 30% reduction in total caloric intake per day, risks to calorie restriction should be minimal. (11) Regarding physical activity, the overwhelming majority of individuals will be able to partake in a walking program with minimal to no risk. More vigorous exercise will be implemented based on baseline fitness and other factors that may impact potential to achieve higher METS. Potential, but unlikely risks include falls or other musculoskeletal injuries resulting from physical activity, or cardiac events among individuals with cardiac disease who engage in overly ambitious exercise regimens in an unsupervised setting. In terms of survey instruments, these risks are also minimal and rare, but include the potential for feelings of discomfort or anxiety related to answering personal questions. Participants will be able to opt out of answering questions that are discomforting to them. For participants completing MREs, there is a risk of feeling anxious or claustrophobic, transient changes in hearing due to clanging of the machine (rare), and risk related to indwelling metal that can be impacted by the machinery, but this will be addressed with proper screening. Lastly there is a risk of breach of confidentiality and privacy associated with being in the study, including potential breach of the FitBit app.

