5.2 EXCLUSION CRITERIA

An individual who meets any of the following criteria will be excluded from participation in this study:

- 1. Other causes of liver disease: Alcohol related liver disease (defined as an average 14 or more drinks per week in men and 7 or more drinks per week in women over the past 12 months); viral hepatitis, autoimmune liver disease, hereditary forms of liver disease, etc.
- Medications known to cause hepatic steatosis or other alternative causes of hepatic steatosis: mediations include steroids, tamoxifen, amiodarone, highly active anti-retroviral therapy (HAART), valproate, methotrexate. Other causes of hepatic steatosis include chronic total parenteral nutrition (TPN), severe rapid weight loss.
- 3. Current or prior history of decompensated cirrhosis: variceal bleeding, ascites, hepatic encephalopathy, or hepatocellular carcinoma.
- 4. Inability to make dietary modifications due to significant medical co-morbidity (including but not limited to severe, uncontrolled diabetes).
- 5. Participation in a pharmacologic clinical trial for NAFLD/NASH.
- 6. Plans for invasive procedures or other regimented lifestyle programs for weight reduction (i.e. bariatric surgery, other structured nutrition or exercise program such as University Metabolic Fitness Program, University of Michigan Medical Weight Loss Program, Weight Watchers, etc)
- 7. Current use of weight reduction medications or supplements.
- 8. Active substance abuse or psychiatric disease which limits patient's ability to follow study protocol.
- 9. Recent cardiovascular event (within last 3 months) including myocardial infarction, percutaneous coronary intervention (PCI), coronary artery bypass graft (CABG), cerebrovascular

accident (CVA), transient ischemic attack (TIA), severe cardiac valve disease, complex arrhythmias, class II-IV New York Heart Association (NYHA) heart failure

- 10. Pregnancy based on self-report
- 11. Individuals randomized to MRE cannot have non-MRI compatible metal in their body or severe claustrophobia.

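### Worsening of a non-liver condition present at screening can be left out of the adverse-event count, against the protocol's own definition of an adverse event

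*Combined protocol and SAP*

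**What the plan says.** Section 8.3.1 defines an AE as "any untoward medical occurrence associated with the use of an intervention in humans, whether or not considered intervention-related". Section 8.3.4 adds that "All AEs occurring while on study must be documented appropriately regardless of relationship".

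The same section then sets out how pre-existing conditions are handled, in three consecutive sentences:

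- The baseline rule: "Any medical condition that is present at the time that the participant is screened will be considered as baseline and not reported as an AE".
- The exception: "if the study participant's condition related to their NAFLD/NASH deteriorates at any time during the study, it will be recorded as an AE".
- The remainder: "Changes in condition in unrelated medical issues with be documented but not reported".

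Section 8.3.5 adds no rule of its own and refers back to this text. Section 9.3.4 promises a summary of adverse events and nothing further.

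On risk, Section 2.3.1 lists "falls or other musculoskeletal injuries resulting from physical activity" and "cardiac events among individuals with cardiac disease who engage in overly ambitious exercise regimens in an unsupervised setting", and describes both as unlikely. Exclusion criterion 9 in Section 5.2 opens with "Recent cardiovascular event (within last 3 months" and goes on to list severe valve disease, complex arrhythmias and NYHA class II to IV heart failure.

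**The concern.** The three sentences give deterioration of a pre-existing condition one route to AE status, and that route is open only to NAFLD/NASH. A participant with stable coronary disease whose angina becomes more frequent, or one with knee osteoarthritis that flares under a rising step goal, has a change in a condition that was there at screening and is not a liver condition. Followed as written, the rule lets staff note the change without counting it as an AE.

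These changes bear directly on the safety of the intervention. The cardiac risk in Section 2.3.1 is stated for people with existing cardiac disease, so part of what one would want to see will take the form of worsening of a baseline condition. Section 5.3 likewise foresees knee pain and osteoarthritis among participants. If such changes are not AEs, the Section 9.3.4 summary undercounts them. Two staff members could also classify the same event differently, one from Section 8.3.1 and the other from Section 8.3.4.

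**Working it through.** No arithmetic applies. The protocol states no rate, prevalence or threshold on this point, so the check is a comparison of the text.

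1. **What *unrelated* refers to.** The sentence directly follows the one on NAFLD/NASH deterioration, so the natural meaning is unrelated to NAFLD/NASH. The alternative, unrelated to the intervention, meets a practical difficulty. Section 8.3.3.2 requires the investigator to judge relatedness for AEs, but a change not yet classed as an AE has no stated route to that judgement. Relatedness would have to be decided before the step that decides it.

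2. **What *reported* refers to.** Two sentences earlier the protocol speaks of a condition not being reported as an AE, and the sentence between speaks of recording as an AE. In that setting, not reported most naturally means not counted as an AE. Since Section 9.3.4 summarises AEs only, a note kept elsewhere would not bring the change into the summary.

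3. **Comparison with the definition.** Section 8.3.1 makes relatedness irrelevant to whether something is an AE, and Section 8.3.4 itself requires documentation of AEs whatever the relationship. Neither leaves out aggravation of an existing disease. The baseline rule and its single exception do so in practice, so the two sections disagree on the same event.

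4. **Whether the affected participants can be enrolled.** Criterion 9 excludes cardiovascular events in the last 3 months and names several severe cardiac conditions. Older or stable coronary disease is not excluded. No criterion excludes joint disease as such; Section 5.1 asks only that the participant report being able to walk a few blocks without help.

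5. **What other sections already catch.**
   - New falls and activity-related musculoskeletal injuries: asked about in the weekly electronic contacts (Section 8.2). Covered.
   - New clinically relevant findings: AEs under Section 7.1. Covered.
   - Serious events judged intervention related: reported under Section 8.3.6. Covered.
   - Non-serious worsening of existing cardiac disease: not new, not serious, and cardiac symptoms are not named in the Section 8.2 focus. Not clearly covered.
   - Non-serious worsening of existing joint disease without a new injury: not clearly covered.
   - Worsening of a non-liver baseline condition judged unrelated to the intervention: outside Section 8.3.6, and left to the disputed sentence.

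The gap is therefore the last three items.

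**The case against.** The strongest reply is that safety recording is broader than one sentence suggests. Falls and activity-related injuries are actively sought, and the investigator asks about AEs at every visit. Section 7.1 counts changes from baseline among clinically significant findings, and unanticipated problems have their own reporting route in Section 8.4.2. A new infarction or sprain is a new event, not a change in an old illness. All of this stands. A reader might infer that the named cardiac and musculoskeletal risks are kept out of AE reporting altogether, or that the AE summary is blind to them. The documents do not support that.

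The second reply is that both key words allow a milder reading. Sections 8.3.3.2 and 8.3.4 use relationship to mean relationship to the intervention, and on that meaning exercise-provoked worsening is not unrelated. In Sections 8.3.6, 8.4.2 and 10.1.7, reporting means submission to the IRB. If that is what is meant here, the events could still be in the summary. This is a fair argument that the wording is ambiguous, but it does not remove the problem: the surrounding sentences point the other way, and nothing tells staff which meaning to apply. It does rule out a claim that data are lost, since the changes are still to be documented.

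The third reply is that the exposed group is narrower than the 3-month window alone suggests, given the other cardiac conditions in criterion 9 and the walking requirement, and that Section 2.3.1 calls these risks unlikely. That is correct and limits the size of the problem. It does not help Section 7.1 close the gap: that section makes only new findings AEs, and a change from baseline prompts a review of management.

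**Conclusion.** The concern holds in a limited form. On its natural reading, Section 8.3.4 allows worsening of pre-existing cardiac or musculoskeletal disease, chiefly when non-serious or judged unrelated, to be left out of the AE count and the Section 9.3.4 summary. This conflicts with Section 8.3.1 and sits badly with the cardiac risk as Section 2.3.1 describes it.

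The conclusion rests on reading *unrelated* as unrelated to NAFLD/NASH and *reported* as counted as an AE. If either word has its milder meaning, the fault is an ambiguity that may be applied inconsistently, and the same edit resolves it.

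The direction of the error is an undercount; its size cannot be stated. The documents do not say how many participants enter with cardiac or joint disease or how often it worsens, and any figure for the number of people affected would not be a count of missed events. Nor do they support the inference that a finding of minimal risk is built in: the safety analysis is descriptive, tests no hypothesis, and has the other routes listed above. The point should be corrected, but it does not threaten the primary comparison.

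**What to change.** Reconcile Sections 8.3.1 and 8.3.4 by replacing the final sentence on pre-existing conditions. The new text should say that any worsening from baseline of a condition present at screening, liver-related or not, is recorded as an AE if it meets Section 8.3.1; that the investigator assesses its causality under Section 8.3.3.2; and that it enters the Section 9.3.4 summary, whether or not it must also be sent to the IRB. A condition that stays as it was at screening remains baseline and is not an AE.

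Separate lines for cardiac and musculoskeletal events in the safety table would be useful but are optional.

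The cost is one replaced sentence and slightly more AE forms. The added burden is small because the protocol already requires these changes to be documented. The edit concerns safety recording only and alters no eligibility criterion, visit or element of the intervention.

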8.3.5 ADVERSE EVENT REPORTING

Adverse event reporting will follow the protocol outlined above.

8.3.6 SERIOUS ADVERSE EVENT REPORTING

The PI will follow the IRBMED standard reporting schedule for SAEs (*https://az.research.umich.edu/medschool/guidance/adverse-event-reporting*). We will report any serious adverse event considered study intervention related.

All SAEs will be followed until satisfactory resolution or until the PI deems the event to be chronic or the participant is stable.

8.3.7 REPORTING OF PREGNANCY

If participant becomes pregnant during study period, participation will end at that time.

8.4 UNANTICIPATED PROBLEMS

8.4.1 DEFINITION OF UNANTICIPATED PROBLEMS

The Office for Human Research Protections (OHRP) considers unanticipated problems involving risks to participants or others to include, in general, any incident, experience, or outcome that meets all of the following criteria:

- Unexpected in terms of nature, severity, or frequency given (a) the research procedures that are described in the protocol-related documents, such as the protocol and informed consent document; and (b) the characteristics of the participant population being studied;
- Related or possibly related to participation in the research ("possibly related" means there is a reasonable possibility that the incident, experience, or outcome may have been caused by the procedures involved in the research); and
- Suggests that the research places participants or others at a greater risk of harm (including physical, psychological, economic, or social harm) than was previously known or recognized.

For guidance on Michigan Medicine UaP guidelines, refer to

https://az.research.umich.edu/medschool/guidance/adverse-events-aes-other-reportable-informationand-occurrences-orios-other.

8.4.2 UNANTICIPATED PROBLEMS REPORTING

The investigator will report unanticipated problems (UaP) to IRBMED (https://az.research.umich.edu/medschool/guidance/adverse-events-aes-other-reportable-informationand-occurrences-orios-other) and will include the following information:

- Protocol identifying information: protocol title and number, PI's name, and the HUM number;
- A detailed description of the event, incident, experience, or outcome;
- An explanation of the basis for determining that the event, incident, experience, or outcome represents an UP;
- A description of any changes to the protocol or other corrective actions that have been taken or are proposed in response to the UP.

To satisfy the requirement for prompt reporting, UPs will be reported using the following timeline:

- UPs that are serious adverse events (SAEs) will be reported to IRBMED according to the standard reporting schedule (within 7-14 days depending on whether it's life threatening serious event vs. other serious adverse event: https://az.research.umich.edu/medschool/guidance/adverseevent-reporting)
- Any other UP will be reported to IRBMED within 14 days of the investigator becoming aware of the problem.

8.4.3 REPORTING UNANTICIPATED PROBLEMS TO PARTICIPANTS

Any UaP that results in a change to the study design, procedures or risks will be addressed as necessary in an amended consent document. Participants will be asked sign the new consent document as indicated.

9 STATISTICAL CONSIDERATIONS

9.1 STATISTICAL HYPOTHESES

Primary Efficacy Endpoint:

We hypothesize that participants who complete the lifestyle intervention (as defined by completing the 6 month return visit and data collection) will achieve reduction in amount of hepatic steatosis (\geq 5% reduction in CAP), with those achieving higher percentage weight loss having larger reductions in amount of steatosis.

Secondary Efficacy Endpoints:

We hypothesize that subjects in the intervention arm will be more likely to achieve weight loss and increase their level of physical activity at 6-month compared to usual care.

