1 PROTOCOL SUMMARY

1.1 SYNOPSIS

Title:	A Randomized Controlled Pilot trial of a Structured Mobile Technology Based Lifestyle Program Vs Usual Care for Patients with Non-Alcoholic
	Fatty Liver Disease
Grant Number:	AWD007197
Study Description:	Lifestyle interventions remain first line therapy for the treatment of
Study Description.	non-alcoholic fatty liver disease (NAFLD). In clinical practice, it is challenging for patients to initiate and maintain these changes. In this randomized clinical pilot trial, we will evaluate impact of a structured mobile technology-based lifestyle intervention program compared to usual care to among patients with NAFLD. We hypothesize individuals randomized to the intervention arm will have significantly improved
	outcomes compared to usual care, and that the intervention will be
	feasible, low cost and amenable to large scale implementation.
Objectives:	Primary objective: compare the effectiveness of usual care to a mobile technology based lifestyle intervention on change in liver and metabolic related parameters.
	Secondary objectives: identify predictors associated with reduction in hepatic steatosis and weight loss.
Endpoints:	Primary Endpoint: change in amount of hepatic steatosis
	Secondary Endpoints: change in weight, change in physical activity
Study Population:	120 adult patients with NAFLD including steatosis only, non-alcoholic steatohepatitis (NASH) and NAFLD-related compensated cirrhosis seen in the Michigan Medicine Hepatology clinic.
Phase or Stage:	N/A
Description of Sites/Facilities Enrolling	
Participants:	Michigan Medicine Hepatology Clinics, and patient identified through
i il cicipantor	Data Direct and EMERSE in various local clinics
Description of Study	
Intervention/Experimental	Personalized adaptive lifestyle intervention program that includes
Manipulation:	physical activity and nutritional feedback compared to usual care
Study Duration:	18 months
Participant Duration:	13 months

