3 OBJECTIVES AND ENDPOINTS

OBJECTIVES	ENDPOINTS	JUSTIFICATION FOR ENDPOINTS
Primary		
Compare the effectiveness of usual care to a mobile technology based lifestyle intervention on change in liver and metabolic related parameters.	Reduction in amount of hepatic steatosis (≥5% overall reduction in CAP score) at 6 months.	Hepatic steatosis is a liver specific outcome that has been shown to improve with diet and exercise and is associated with risk of downstream clinical outcome such as development of NASH and cirrhosis.
Secondary		

OBJECTIVES	ENDPOINTS	JUSTIFICATION FOR ENDPOINTS
Improvements in other liver-specific and metabolic outcomes	weight loss, increase in total physical activity (based on step counts)	Weight loss has been associated with histologic improvements in NAFLD and NASH. Physical activity has been shown to improve fibrosis, liver enzymes, metabolic parameters and HRQOL.

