4 STUDY DESIGN

4.1 OVERALL DESIGN

This randomized clinical pilot trial will compare a mobile technology-based lifestyle intervention to a waitlist control group receiving usual care for adult patients with NAFLD. The intervention will use FitBit to track and promote physical activity through tailored longitudinal feedback. Patient will also receive nutritional counseling with serial nutritional assessments. The primary endpoint will be change in amount of hepatic steatosis. Secondary outcomes include changes in weight and physical activity (assessed by trend in step counts). A wait-list control design will be applied. 60 Patients will be randomized to the intervention arm for 6 months and 60 to usual care (the wait-list control). Those initially randomized to the intervention arm will then transition to a 6-month post intervention monitoring period to assess maintenance of behavior change and sustainability of impact on outcomes of interest. Individuals initially randomized to usual care, will transition to the intervention at month 6 for a total of 6 months.

The intervention arm will receive tailored physical activity and nutritional counseling, and the waitlist control arm which will follow usual and customary care for NAFLD patients attending our Heptology clinic for 6 months and then receive the 6-month intervention.

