4.2 SCIENTIFIC RATIONALE FOR STUDY DESIGN

This trial will incorporate a wait-list control that will allow us to maximize our ability to assess the primary outcome (by using a pre-post intervention analysis). The 6-month post-intervention follow-up among those initially randomized to the intervention will allow us to assess maintenance of behavior change.

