9.2 SAMPLE SIZE DETERMINATION

Sample size calculations will be made based on the total N for the cohort. Enrollment of 120 patients in the intervention should provide adequate power to assess for parameters associated with \geq 5% reduction in steatosis and weight loss using 80% power, alpha 0.05. We anticipate a dropout rate of up to 20%.

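### The primary hypothesis in 9.1 concerns intervention completers with no comparator, and 9.3.2 states no between-arm CAP contrast, although the stated objective is a randomised comparison with usual care

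*Combined protocol and SAP*

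**What the plan says.** Three places set up a randomised comparison. The synopsis (1.1) begins its hypothesis "We hypothesize individuals randomized to the intervention arm will have significantly improved" and completes it with outcomes relative to usual care. The primary objective (section 3) is to "Compare the effectiveness of usual care to a mobile technology based lifestyle intervention on change in liver and metabolic related parameters", and the endpoint beside it is "Reduction in amount of hepatic steatosis (≥5% overall reduction in CAP score) at 6 months". Section 4.1 says the trial "will compare a mobile technology-based lifestyle intervention to a waitlist control group receiving usual care", with 60 patients randomised to each arm.

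The statistical sections differ. The primary hypothesis in 9.1 reads "We hypothesize that participants who complete the lifestyle intervention (as defined by completing the 6 month return visit and data collection) will achieve reduction" in steatosis of at least 5% in CAP, with larger reductions in those who lose more weight. It names no comparator. The secondary hypotheses in the same section do: participants in the intervention arm are to lose weight and "increase their level of physical activity at 6-month compared to usual care".

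Section 4.2 says the wait-list design will "maximize our ability to assess the primary outcome (by using a pre-post intervention analysis"). Section 9.2 takes the total cohort, describes 120 patients as being in the intervention, and says this "should provide adequate power to assess for parameters associated with" response. Section 9.3.2 gives the CAP measure, the 5% threshold at 6 months with maintenance at 12, a modified intention-to-treat analysis and a separate analysis of those with complete data. It names no contrast between arms, no test and no model. It also removes from the final analysis anyone randomised who never supplied FitBit data.

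**The concern.** An analyst who follows 9.1 would ask whether people who finished the intervention improved from baseline. The primary objective asks whether they improved more than they would have under usual care. The first question can be answered yes with no intervention effect at all, if CAP falls over time in both arms, if high baseline values regress towards the mean, or if those who return at 6 months are the ones doing well. The protocol's own background (2.2) warns that control groups in this disease vary in how they take up diet and exercise advice, and usual care as described in 6.1.1 includes brief lifestyle advice. Both arms have VCTE at baseline and month 6, so the data for the controlled comparison will exist; the plan does not say they will be used that way for CAP.

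The FitBit rule adds a second problem. Whether someone ever provides FitBit data is known only after randomisation and depends on being given a device. Section 6.1.1 gives it to the 60 people in the intervention arm. Table 2 in 1.3 marks provision for the wait-list arm at visits 1 and 2, in a row whose label refers to the intervention arm. When controls receive a device, and so when they could first satisfy the rule, is unclear.

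**Working it through.** **The plan's own figure.** Section 9.2 gives N = 120, 80% power, alpha 0.05 and dropout of up to 20%. It gives no effect size, SD, response rate or number of predictors, so 120 can be neither reproduced nor refuted.

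**The sections side by side.**

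| Section | Population | Comparator for CAP |
|---|---|---|
| 1.1, 3, 4.1 | randomised arms | usual care |
| 9.1 primary | intervention completers | none |
| 4.2 | not stated | own baseline (pre-post) |
| 9.2 | total cohort | none (predictors of response) |
| 9.3.2 | modified ITT; completers | none stated |
| 9.3.6, 9.3.7 | subgroups; individual listings | none stated; pre-post |

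Section 9.3.1 adds only two-tailed testing at 0.05. No section supplies the missing CAP contrast.

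**What an uncontrolled test could show with no intervention effect.** Completers in one arm after dropout: 60 × 0.8 = 48. Assumed, not in the documents: downward drift 3-10 dB/m, SD of 6-month change 20-50 dB/m, normally distributed changes. One-sample t test of mean change, two-sided 0.05, 47 degrees of freedom, critical value 2.01, noncentrality = drift/SD × √48:

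- Drift 3, SD 50: 3/50 × 6.93 = 0.42; probability of significance 0.07.
- Drift 3, SD 20: 3/20 × 6.93 = 1.04; 0.17.
- Drift 10, SD 50: 10/50 × 6.93 = 1.39; 0.27.
- Drift 10, SD 20: 10/20 × 6.93 = 3.46; 0.92.
- Drift 0, either SD: 0.05.

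Drift common to both arms cancels in a between-arm comparison.

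**What the randomised comparison can detect.** 48 per arm, two-sided 0.05, 80% power, unadjusted. For two proportions (z test with pooled variance under the null), by assumed control response rate:

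| Control rate | Detectable difference | Power for +20 points |
|---|---|---|
| 10% | 23.3 points | 0.69 |
| 20% | 26.6 | 0.57 |
| 30% | 28.0 | 0.52 |
| 40% | 28.1 | 0.50 |
| 50% | 27.2 | 0.52 |

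For a difference in means, the normal approximation (1.960 + 0.842) × √(2/48) gives 0.57 SD; the two-sample t calculation gives 0.58 SD.

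**The case against.** The best reply is that the intent is not in doubt. Three sections state a comparison with usual care, and section 3 sets it beside the month-6 CAP endpoint. A pre-post analysis, as in 4.2, is compatible with comparing pre-post changes between arms, and the words randomised and intention to treat in 9.3.2 suggest an arm structure. The trial is also labelled a pilot. Much of this stands. A reader might infer that the plan has no governing comparison at all; the documents do not support that, because the objective is clear and 9.1 is the sentence out of line. But 9.1 and 9.3.2 are the sections an analyst follows, and neither carries the objective through. Pilot status does not settle it either, since the synopsis expects significant improvement and 9.3.1 sets a significance level.

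A reader might also infer that measurement noise alone would produce false credit, because it carries some people past the 5% line. Noise without drift leaves a pre-post test of mean change at its 5% error rate, and 9.1 names no response rate or test that would count as success. A share of responders is not an error rate.

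Finally, a reader might size the FitBit exclusion at 12 of 60 controls (20% of 60). The 20% in 9.2 has no arm and no timing, and Table 2 marks a device for the wait-list arm at visit 1. Controls lost before visit 2 would usually lack month-6 CAP anyway, while controls who attend but never provide data would be excluded on top. The 12 is neither an estimate nor a ceiling.

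**Conclusion.** The point holds and should be corrected before outcome data are seen. The primary hypothesis does not match the primary objective, and the analysis section does not repair the mismatch. Followed as written, 9.1 together with the FitBit rule would not give an unbiased answer to the primary objective.

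This rests on the text alone. The 7%-92% range shows how far a pre-post test could mislead if CAP drifts; it depends wholly on assumed drift and SD, and falls to 5% with no drift. The direction and size of any bias from the FitBit exclusion cannot be derived from the documents.

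**What to change.** 1. In 9.1 and 9.3.2, make the primary analysis the month-6 comparison of CAP response (the 5% criterion in section 3) by randomised arm in all randomised participants, adjusted for baseline CAP. Report baseline-adjusted continuous CAP change alongside, since 1.1, 4.1 and 9.3.2 describe the outcome as change.
2. In 9.3.2, delete the FitBit-data exclusion from the primary analysis and state how missing month-6 CAP is handled. Section 7.2 allows replacement of people randomised but not treated; keep those who are replaced in the arm to which they were randomised.
3. In 4.2 and 9.3.2, label the pre-post, completer, weight-loss association and 12-month maintenance analyses as secondary. By 12 months the wait-list arm has had the intervention, so no usual-care comparator remains.
4. In 9.2, correct the description of 120 patients in the intervention to 60 per arm at randomisation (120 only once the wait-list arm crosses over). Add what 48 per arm can detect at 80% power, two-sided 0.05: about 23-28 points over assumed control rates of 10%-50%, or about 0.58 SD, both unadjusted.

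The cost is text edits to 4.2, 9.1, 9.2 and 9.3.2. No patients or visits are added, because VCTE is already scheduled at visits 1 and 2 in both arms. The downside is that the primary claim becomes harder to meet: power for a 20-point difference is only about 50%-69% over those control rates.
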